2.3 Sample Size and Power

Seven LGMD2D subjects with a-SG deficiency by muscle biopsy or DNA testing will be enrolled at Nationwide Children's Hospital for the gene transfer study:

- Cohort 1A: One (n=1) adult LGMD2D wheelchair-dependent subject will receive single-limb perfusion at the low dose: 1x10¹² vg/kg per lower extremity.
- Cohort 1B: Three (n=3) LGMD2D subjects will receive bilateral whole limb perfusion at the low dose: 1x10¹² vg/kg per lower extremity.
- Cohort 2: Three (n=3) LGMD2D subjects will receive bilateral whole limb perfusion at the high dose: 3x10¹² vg/kg per lower extremity.

If safety data is satisfactory at low dose in single limb (Cohort 1A), the same dose will be used for bilateral lower limb infusion (Cohort 1B). With satisfactory safety data, high dose will be used for bilateral lower limb infusion (Cohort 2).

3. Efficacy and Safety Endpoints

3.1 Primary Efficacy Endpoints

Not applicable.

3.2 Secondary Efficacy Endpoints

• Six-minute walk test (6MWT)

Document Date: 25Apr2022 CONFIDENTIAL Page 7 of 15

Sponsor Name: Sarepta Therapeutics, Inc.

Sponsor Protocol ID: 9004-101 Covance Study ID: 000000209191

3.4 Safety Endpoints

- Adverse events
- Laboratory assessments including hematology, chemistry, and urinalysis
- Vital signs
- Physical examination
- Immunology response to rAAVrh74 and hSGCA
 - Anti-AAVrh74 Antibody Titer
 - T-Cell Response to ELISpot Peptide Pools (Number of Spot Forming Cells per Million peripheral blood mononuclear cells [PBMC])
 - AAVrh74 Peptide Pool 1 of 3
 - AAVrh74 Peptide Pool 2 of 3
 - AAVrh74 Peptide Pool 3 of 3
 - hSGCA Peptide Pool 1 of 1
 - GFP Peptide Pool (Negative Control)
 - DMSO (Blank)

4. Analysis Populations

4.1 Full Analysis Set (FAS)

The Full Analysis Set includes all subjects who are enrolled and receive gene transfer.

5. Data Handling

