In an attempt to dampen the host immune response to our AAV-based therapy, subjects will be started on a prophylactic daily dose of prednisone (or alternative glucocorticoid in dose equivalency) at approximately 1mg/kg/day with a maximum dose of 60 mg/day. Post-treatment, we may increase this dose to approximately 2 mg/kg/day with a maximum dose of 60 mg/day, depending on T cell responses measured by ELISpot assay. Treatment will be initiated one day prior to the gene transfer and the subjects will remain on prednisone treatment for approximately one month. A tapering protocol for prednisone will be implemented based on individual subjects' immune response to the gene transfer, again assessed by the ELISpot assay. If GGT elevations are seen after 30 days; the prednisone treatment will be continued or restarted at an appropriate dose for duration necessary to quell the immune reaction with a maximum of 60 mg per day. The duration of treatment will be determined based on weekly levels of GGT and immune responses.

Subjects will be admitted to the Nationwide Children's Hospital the day of the gene transfer. Procedures will be performed under sterile conditions in the Cardiac Catheterization Suite. An intravenous catheter with heparin lock will be placed in the arm for delivery of sedation.

I. Injection Preparation

Preparation of the scAAVrh74.tMCK.hSGCA gene vector will be done by the Nationwide Children's Hospital research pharmacist according to the Manual of Operating Procedures

(MOOP). Immediately prior to transportation to the clinical setting, appropriate dilutions of the test article will be completed by the pharmacy. [REDACTED]

[REDACTED]

[REDACTED]

Documentation of the dilution will be completed by the pharmacy following standard pharmacy protocol.

The vector-containing syringes will be delivered to the designated Cardiac Catheterization Suite at Nationwide Children's Hospital. It will be delivered under ambient temperature (not frozen) and administered to the subject within 8 hours of preparation. Handling of scAAVrh74.tMCK.hSGCA gene will follow compliance standards for Biosafety Level 1 vectors.

http://www4.od.nih.gov/oba/RAC/guidelines_02/APPENDIX_G.htm#_Toc7246561

II. Vector Administration Protocol

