The overall procedure is such that the vector will be delivered via direct intravascular delivery into the femoral artery of the leg followed by an 8-10 minute dwell time.¹ Subjects will undergo appropriate anesthesia (general or conscious sedation as appropriate) for their age and muscle disease per Children's Hospital Department of Anesthesia protocol. Under sterile conditions, the following protocol will be performed:

- a. The subject is transferred from a hospital bed to the Cardiac Catheterization Lab and positioned in the usual supine manner, attached to appropriate monitoring and placed under general anesthesia or conscious sedation as determined by the anesthesiologist

utilizing NCH anesthesia protocols that minimize the risk of anesthetic reaction in muscular dystrophy. The subject will be prepped and draped in the usual sterile fashion. A baseline activated clotting time (ACT) level will be obtained from a peripheral IV.

- b. The femoral artery and femoral vein will be entered percutaneously using the Seldinger technique and guide wire advanced and positioned under fluoroscopy. A sidearm sheath will be advanced over the guide wire—one into the femoral artery and one into the femoral vein and both flushed with heparinized normal saline. Before the occlusion balloons are inserted through the sidearm sheaths, 200 IU/kg of heparin will be administered via a peripheral arm IV and allowed to circulate for 3-5 minutes, at which time a blood sample will be drawn from the peripheral IV and an ACT will be measured with the goal of > 200 seconds from an anticipated base line of 90-120 seconds drawn systemically (arm-PIV). If the post heparin ACT is less < 200 seconds, a second dose of heparin, 50-100 IU /Kg will be administered. An immediate follow up ACT will be obtained with the targeted ACT goal of > 200 seconds. This process will be repeated until ACT's are within the designated range and repeated every 30-60 minutes to assess ongoing anticoagulation levels.
- c. The procedure for vascular delivery of scAAVrh.74tMCK.hSGCA to the isolated limb can be summarized as follows:
 - The area near the inguinal ligament will be infused with several mLs of Marcaine or Lidocaine for local anesthetic effect. Percutaneous access of the femoral artery will be obtained using the Seldinger technique and advancing an introducer and dilator

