over a guide wire. The dilator and wire are removed and sidearm sheath (REF CP-08403; Manufacturer: Arrow) placed and flushed appropriately with heparinized normal saline.

- Percutaneous access of the femoral vein is obtained in a similar fashion.
- Both sets of femoral vessels (right and left, artery and vein) will be cannulated before heparinization of the subject.
- Before the occlusion balloons are inserted through the sidearm sheaths, 200 IU/kg of heparin will be administered via a peripheral arm IV and allowed to circulate for 3-5 minutes, at which time a blood sample will be drawn from the peripheral IV and an ACT will be measured with the goal of > 200 seconds from an anticipated base line of 90-120 seconds drawn systemically (arm-PIV). If the post heparin ACT is less < 200 seconds, a second dose of heparin, 50-100 IU /Kg will be administered. An immediate follow up ACT will be obtained with the targeted ACT goal of > 200 seconds. This process will be repeated until ACT's are within the designated range.
- Using fluoroscopic guidance a Tyshak II Balloon Dilation catheter is advanced over a guide wire through the sheath into the femoral artery above the take-off of the femoral profunda artery and positioned to achieve arterial stasis when the occlusive balloon is inflated. Positioning the arterial balloon catheter above the femoral profunda artery take off enables perfusion and targeting of proximal muscles of the hip via the anterior circumflex artery.

- Again with fluoroscopic guidance a Tyshak II Balloon Dilation catheter is advanced over a guide wire through the sheath into the femoral vein to approximately the same level as the arterial balloon catheter and positioned to achieve venous stasis when the balloon is inflated.
- If needed a tourniquet may be placed over the region of the balloons to augment vascular stasis and isolation of the limb circulation.

- [REDACTED]
[REDACTED]
- [REDACTED]
[REDACTED]
[REDACTED]
[REDACTED]
[REDACTED]
[REDACTED]
[REDACTED]
[REDACTED]
[REDACTED]
[REDACTED]
[REDACTED]
[REDACTED]
[REDACTED]
[REDACTED]
[REDACTED]

Subjects will be monitored for bleeding, perfusion to the extremity, compartment syndrome and neuromuscular integrity. Compartment syndrome will be assessed by direct limb palpation and Doppler ultrasound (as needed). Neuromuscular integrity will be determined by routine assessment of clinical pain and strength.

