5.1 Time Points and Visit Windows

Day 1 is defined as the day when subjects received gene transfer. Relative days after Day 1 are calculated as (assessment date – Day 1 date) + 1. Relative days prior to Day 1 are calculated as (assessment date – Day 1 date). The day prior to Day 1 is Day -1.

The baseline value will be defined as last scheduled or unscheduled value collected prior to Day 1, unless otherwise specified. For post-baseline, only data from scheduled visits will be included in the summary tables.

Sponsor Name: Sarepta Therapeutics, Inc.

Sponsor Protocol ID: 9004-101 Covance Study ID: 000000209191

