6.6 Safety Analyses

All safety analyses will be performed using FAS.

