6.6.2 Adverse Events

Adverse events (AEs) will be coded using the Medical Dictionary for Regulatory Activities (MedDRA) [Version 22.0].

AEs will be graded by the Investigator as follows:

- Grade 1: Mild; asymptomatic or mild symptoms; clinical or diagnostic observations only; intervention not indicated
- Grade 2: Moderate; minimal, local or noninvasive intervention indicated; limiting age-appropriate instrumental activities of daily living (ADL)*
- Grade 3: Severe or medically significant but not immediately life-threatening; hospitalization or prolongation of hospitalization indicated; disabling; limiting self-care ADL**
- Grade 4: Life-threatening consequences; urgent intervention indicated

Sponsor Protocol ID: 9004-101 Covance Study ID: 000000209191

Grade 5: Death related to AE

A Semi-colon indicates 'or' within the description of the grade.

- *Instrumental ADL refer to preparing meals, shopping for groceries or clothes, using the telephone, managing money, etc.
- **Self-care ADL refer to bathing, dressing and undressing, feeding self, using the toilet, taking medications, and not bedridden.

The relationship between an AE and study drug is assessed as definite, probable, possible, unlikely, or not related. A treatment-related AE is an AE considered by the investigator as definitely, possibly, or probably related to study drug or with unknown/missing relationship to study drug.

All AE data recorded in eCRF will be listed. In addition, a listing of serious AEs (SAEs) will be produced.

Treatment-emergent AEs (TEAEs) will be summarized by cohort and overall. TEAEs are AEs that occur or worsen in severity on or after gene transfer. AEs with missing start date will be considered as TEAEs.

TEAEs will be summarized by cohort and overall. An overview table will summarize the number and percentage of subjects with at least one of the following TEAEs, where subjects with more than one TEAE in a particular category are counted only once in that category:

- Any TEAE
- TEAE by maximum severity grade
- Treatment-related TEAE
- Any treatment-emergent SAE (TESAE)
- Treatment-related TESAE
- TESAE leading to death

The number of total TEAEs will be also included in the overview table.

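### The only analysis set requires receipt of gene transfer and AE tables start there, so a subject harmed during preparation and not infused is missing from every AE summary table

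*SAP*

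**What the plan says.** **Analysis set.** SAP section 4 contains a single population, in 4.1: "The Full Analysis Set includes all subjects who are enrolled and receive gene transfer". SAP 6.6 then states: "All safety analyses will be performed using FAS".

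**Event window.** SAP 6.6.2 builds its AE tables on treatment-emergent events: "TEAEs are AEs that occur or worsen in severity on or after gene transfer". It adds one default: "AEs with missing start date will be considered as TEAEs". The time origin in SAP 5.1 has the same anchor: "Day 1 is defined as the day when subjects received gene transfer".

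**What comes before vector.** Protocol 6.3 says of prednisone: "Treatment will be initiated one day prior to the gene transfer". On the day itself: "Subjects will undergo appropriate anesthesia (general or conscious sedation as appropriate"). Then comes vascular access: "Both sets of femoral vessels (right and left, artery and vein) will be cannulated before heparinization of the subject". Heparin follows, then balloon isolation of the limb, and only then vector.

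**What is collected.** Protocol 8.1 collects adverse events from enrolment to the last visit. It grades relatedness separately to study agent, study procedures and pre-existing disease.

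**What else is reported.** SAP 6.6.2 lists all recorded AE data and produces an SAE listing. SAP 6.2 tabulates enrolled subjects, FAS subjects and reasons for discontinuation.

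**The concern.** The primary objective (protocol 4.1, SAP 2.1.1) covers the route of administration as well as the vector. Protocol 11.3.2 describes real hazards in the preparatory steps: anaesthetic complications, puncture-site haematoma that may need transfusion or surgery, vessel blockage and contrast reactions. The tabulated safety population is conditioned on preparation having gone far enough to infuse. Where a complication is the reason the infusion did not happen, that condition selects on the outcome being measured.

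A second, smaller gap affects infused subjects. Events starting on the prednisone day before transfer are collected but are not treatment-emergent unless they worsen afterwards.

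With seven subjects, one missing case decides whether a table shows none or one.

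**Working it through.** **1. Planned number.** SAP 2.3: 1 (Cohort 1A) + 3 (1B) + 3 (2) = 7. This reproduces. The readable text gives no power calculation, and none is needed here.

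**2. Tracing one case through the rules.** Suppose a subject has a serious complication during anaesthesia, cannulation, heparinisation or balloon placement, and no vector is given.
- FAS membership (SAP 4.1): not met, because gene transfer was not received.
- Safety tables (SAP 6.6): FAS only, so the subject is excluded.
- TEAE status (SAP 6.6.2) and Day 1 (SAP 5.1): there is no gene transfer to anchor either.
- Missing-date default (SAP 6.6.2): it can make an event treatment-emergent, but it does not bring a subject into the FAS.
- Listings (SAP 6.1, 6.6.2) and disposition (SAP 6.2): the case could appear here.

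The case is therefore absent from all AE summary tables but not necessarily from all reporting.

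**3. Infused subjects.**
- Event on the prednisone day before transfer: outside the tables unless it worsens on or after transfer.
- Event on the day of transfer but before vector: it counts if status is set by calendar date, and does not if set by clock time. SAP 6.1 gives a date format, but no section states the rule.

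**4. Size for one uninfused, harmed subject.** Assumptions: exactly one such case, no other subject with the event, and the FAS as denominator. The documents state no replacement rule, so both versions are shown. The intervals are exact (Clopper-Pearson) 95% limits added here; the SAP plans counts and percentages only. For zero events the upper limit is 1 − 0.025^(1/n).

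| | FAS table | All subjects in whom preparation began |
|---|---|---|
| Not replaced, overall | 0/6 = 0% (upper limit 45.9%) | 1/7 = 14.3% (0.4% to 57.9%) |
| Replaced, overall | 0/7 = 0% (upper limit 41.0%) | 1/8 = 12.5% (0.3% to 52.7%) |
| Not replaced, cohort of 3 | 0/2 = 0% | 1/3 = 33.3% |
| Replaced, cohort of 3 | 0/3 = 0% | 1/4 = 25.0% |

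**5. How likely is such a case?** The documents give no non-infusion rate. For an assumed per-subject rate p, the chance of at least one uninfused subject in seven is 1 − (1 − p)^7:
- p = 1%: 6.8%
- p = 2%: 13.2%
- p = 5%: 30.2%
- p = 10%: 52.2%

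These cover stopping for any reason, harmful or not.

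**The case against.** The strongest reply is that little is hidden. The SAP lists all recorded AEs and all SAEs, and disposition shows enrolled against FAS counts, so a gap of one would be visible. Protocol 8.3 sends every SAE to the DSMB within 48 hours regardless of relatedness. In a seven-subject descriptive trial the listings carry much of the safety message, and an as-treated set is a defensible basis for vector safety. This stands as a limit on the point: a reader might infer that the case vanishes from the safety result, and the documents do not support that. However, SAP 6.6 does not say that listings reach beyond the FAS, and the summary tables are where rates will be read.

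Four further inferences also go too far.
- *The exclusion always flatters safety.* It does not. If an infusion is stopped without harm, leaving that subject out raises rates: one event among seven infused is 1/7 = 14.3% in the FAS, against 1/8 = 12.5% if the unharmed subject is counted.
- *The protocol's own risks size the gap.* Section 11.3.2.2 puts haematoma below 4% and vessel block or damage below 0.5%. Read per subject, the chance of at least one in seven is up to 1 − 0.96^7 = 24.9% or 1 − 0.995^7 = 3.4%. These are chances of a complication, and nothing links them to abandoning an infusion. Counting per vessel (6 × 4 + 1 × 2 = 26) would give higher figures with the same flaw, and would also assume that vessels within one subject are independent.
- *An uninfused subject would be replaced to keep seven.* No such rule is stated.
- *All same-day preparatory events are lost for infused subjects.* They may well count if status is set by date.

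Finally, the protocol sometimes uses gene transfer for the whole procedure (the title of 6.3, and 11.3.2.5). On that reading a subject whose procedure was begun might belong to the FAS. Receipt of vector is the more natural reading, but the SAP leaves the term undefined and does not address partial or one-limb infusion.

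**Conclusion.** The point holds for the AE summary tables. A subject harmed in preparation and not infused is in none of them, and for infused subjects prednisone-day events are outside the window unless they worsen. Reading gene transfer as receipt of vector, one such case moves the overall figure from 0% to 14.3% or 12.5%, and a three-subject cohort from 0% to 33.3% or 25.0%, depending on an unstated replacement rule.

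Whether this matters in practice is unknown. The SAP is dated 25 April 2022, after enrolment was planned to end in December 2017, and the documents do not say whether every prepared subject was infused. If all were, the restriction to the FAS changes nothing and only the event window remains. This is an inexpensive improvement to make, and the documents do not show that any result is wrong.

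**What to change.** - **SAP section 4:** add a Safety Set of all enrolled subjects in whom a protocol-required infusion step was begun (first prednisone dose or start of anaesthesia or sedation), whether or not vector was given.
- **SAP 6.6 and 6.6.2:** run the AE summaries on that set, count events from that first step, and show pre-infusion and post-infusion events separately.
- **Keep the FAS** for the 6MWT and for safety tables restricted to vector-exposed subjects.
- **Clarify in the same edit:** what receiving gene transfer means, including partial or one-limb infusion; whether same-day events are classified by date or clock time; and that the AE and SAE listings cover all enrolled subjects.

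**Cost.** SAP wording and one extra set of AE tables. No new data are needed, because events are collected from enrolment. The drawback is that subjects without vector exposure enter the denominator, which could lower some percentages if an infusion was stopped without harm; the separate display and the retained FAS tables keep that visible. If every prepared subject was infused, the sponsor can say so, and only the event window changes.

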5.1 Time Points and Visit Windows

Day 1 is defined as the day when subjects received gene transfer. Relative days after Day 1 are calculated as (assessment date – Day 1 date) + 1. Relative days prior to Day 1 are calculated as (assessment date – Day 1 date). The day prior to Day 1 is Day -1.

The baseline value will be defined as last scheduled or unscheduled value collected prior to Day 1, unless otherwise specified. For post-baseline, only data from scheduled visits will be included in the summary tables.

Sponsor Name: Sarepta Therapeutics, Inc.

Sponsor Protocol ID: 9004-101 Covance Study ID: 000000209191

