Laboratory tests with values within the clinically significant range will be repeated during the same visit whenever possible (refer to Table 6.4 for a complete list of clinically significant range values). If the test result returns after the subject leaves the clinic, they will be immediately contacted. For local residents they will be asked to return to the outpatient clinic for a repeat test as clinically indicated. For non-local residents, arrangements will be made to have the blood test redrawn in a laboratory close to home or by their primary care physician. To avoid any confusion for the primary care physician, they will be informed (with permission from the subject) of their participation in the study at the time of gene transfer. If the AE requires treatment, this will be carried out by the primary care physician or a doctor of choice selected by the subject. We will obtain copies of repeat laboratory tests and any relevant medical records for addition to the subject’s research chart.

Only those adverse events requiring treatment will qualify as DLT. The PI will fulfill the reporting responsibilities under 21 CFR 312.32(c), to notify FDA in an IND safety report of potentially serious risks, as soon as possible, but no later than 15 calendar days after the investigator receives the safety information and determines that the information qualifies for reporting. The investigator will confer with the DSMB and FDA before continuing enrollment.

Table 6.4 Clinically Significant Laboratory Range

Test	Units	Reference Range		Clinically Significant Range
Hemoglobin	g/dL	2Y – 5Y	11.5 – 13.5	< 8.0 or > 18
		6Y – 11Y	11.5 – 15.5	
		12Y – Adult	12.0 – 16.0	
WBC	K/cu mm	4Y – 5Y	5.5 – 15.5	≤3.5 or ≥ 20
		6Y – 9Y	5.0 – 14.5	
		10Y – 20Y	4.5 – 13.5	
		21Y – Adult	4.5 – 11.0	
BUN	mg/dL	5 - 18		≥35
PT	sec	12.4 – 14.7		≤ 5.0 or ≥ 35.0
PTT	sec	24 - 36		≥ 125
Platelet	K/cu mm	140 - 440		≤ 90 or ≥ 800
Amylase	U/L	0 – 17Y	<110	≥ 200
		18Y – Adult	30 - 110	
Total Protein	g/dL	3Y – 15Y	5.8 – 8.7	≤4.4 or ≥ 9.5
		16Y – Adult	6.4 – 8.4	
Total Bilirubin	mg/dL	0.1 – 1.0 mg/dL		≥ 3.0
Creatinine	mg/dL	4Y – 7Y	0.3 – 0.8	≥ 1.8
		8Y – 10Y	0.3 – 0.9	
		11Y – 12Y	0.4 – 1.0	
		13Y – 17Y	0.5 – 1.2	
		18Y – Adult	0.6 – 1.3	
GGT*	U/L	8 – 78		3XULN

ULN= upper limit normal

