11.3.2.11 MYOGLOBINURIA/RHABDOMYOLYSIS

There have been cases where myoglobinuria as a result of rhabdomyolysis has occurred after ILP infusion of scAAVrh74.tMCK.hSGCA. There is an increased risk of this due to the disease state of LGMD2D, but there have been cases seen in the subjects within this study. This is thought to possibly be caused by the increase in muscle strength after gene transfer that leads subjects to exercise more rigorously. Subjects will be asked to decrease exercise to a low to moderate level following the transfer and to visually monitor their urine for any brown discoloration. Subjects will also be warned to avoid over-exhaustion and to stay well hydrated. If brown urine discoloration or muscle pain were to occur, they should alert the PI as soon as possible or go to the nearest Emergency Room.

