6.6.3 Laboratory Evaluations

All laboratory data recorded in eCRF will be listed.

The observed laboratory data, change from baseline, and percent changes from baseline for the following hematology and general chemistry laboratory tests will be summarized using standard descriptive statistics by cohort and overall, and by visit. For urinalysis laboratory tests listed below, the number and percentage of subjects with each assessment category will be presented.

Laboratory Category	Laboratory Test
Hematology	White blood cell (WBC), Hemoglobin, Hematocrit, Platelet count, Mean corpuscular volume (MCV), Mean corpuscular hemoglobin (MCH), Mean corpuscular hemoglobin concentration (MCHC), Red cell distribution width (RDW), Red blood cell (RBC), Neutrophil, Segmented neutrophil, Lymphocyte, Monocyte, Eosinophils, Basophils, Bands, Mean platelet volume (MPV)
Chemistry	Sodium, Potassium, Chloride, Carbon dioxide, Blood urea nitrogen (BUN), Creatinine, Glucose, Total protein, Total bilrubin, Alanine aminotransferase (ALT), Aspartate aminotransferase (AST), Alkaline phosphatase (ALP), Gamma glutamyl transferase (GGT), Amylase, Creatine kinase (CK), Cystatin C, Prothrombin time (PT), International normalized ratio (INR), Activated partial thromboplastin time (aPTT), Fibrinogen
Urinalysis	Color, Appearance, Specific gravity, pH, Protein, Glucose, Ketones, Bilirubin, Occult Blood, Nitrite, Urobilinogen, Leukocyte Esterase, Microscopic Urine, RBC, WBC, Mucus, Epithelial Cells Specimen Microscopic Examination

Line plots of liver function tests including ALT, AST, total bilurubin, GGT, total protein, ALP, platelets, INR, and PT over time will be created by subject.

The eDISH (evaluation of Drug-Induced Serious Hepatotoxicity) plots will be provided, ALT (x baseline) and GGT (x upper limit of normal [ULN]) will be plotted against total Bilirubin (x ULN) based on maximum elevation any time post baseline.

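### Unscheduled peaks in CK, creatinine, cystatin C and other tests outside the liver displays reach no laboratory summary or plot, only listings

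*SAP*

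**What the plan says.** SAP 5.1 treats the two sides of the comparison differently. Before gene transfer any result can count: "The baseline value will be defined as last scheduled or unscheduled value collected prior to Day 1, unless otherwise specified". Afterwards the rule is: "For post-baseline, only data from scheduled visits will be included in the summary tables".

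SAP 6.6.3 then says that observed values, changes and percent changes in hematology and chemistry "will be summarized using standard descriptive statistics by cohort and overall, and by visit". CK, creatinine, cystatin C and BUN are in the chemistry list; WBC and hemoglobin are in the hematology list. The readable SAP contains no worst-value, shift or clinically-significant-range table.

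Two further displays are planned. The eDISH plots use the largest post-baseline elevation and cover ALT, GGT and total bilirubin. The per-subject plots are specified as "Line plots of liver function tests including ALT, AST, total bilurubin, GGT, total protein, ALP, platelets, INR, and PT over time". Separately, "All laboratory data recorded in eCRF will be listed".

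Protocol 11.3.2.11 says of myoglobinuria and rhabdomyolysis that "there have been cases seen in the subjects within this study". It tells subjects with brown urine or muscle pain to contact the investigator or go to an emergency room.

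**The concern.** Safety is the primary objective, and SAP 3.4 names laboratory assessments as a safety endpoint distinct from adverse events. A result drawn between visits is usually drawn because something has happened, so it is informative. A table that leaves out such results tilts toward showing no toxicity.

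The SAP in effect recognises this for the liver, where eDISH takes the worst value whenever it occurred. The same logic is not carried over to muscle and renal tests, although muscle breakdown is a risk the protocol reports as already observed. A reader of the laboratory tables could see unremarkable CK and creatinine at every visit while the highest values recorded in the study sit only in a listing.

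**Working it through.** **Step 1. Which displays can show an unscheduled post-baseline result?**

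| Tests | By-visit table | eDISH (worst value) | Per-subject line plot | Listing |
|---|---|---|---|---|
| ALT, GGT, total bilirubin | no | yes | planned | yes |
| AST, ALP, total protein, platelets, INR, PT | no | no | planned | yes |
| CK, creatinine, cystatin C, BUN, WBC, hemoglobin | no | no | none | yes |

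The SAP 5.1 restriction applies to summary tables, so it does not bar unscheduled results from plots. The SAP does not state that the line plots include them. For the last row the listing is the only output.

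**Step 2. Which protocol routes produce off-schedule results for those tests?**

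- *Repeat tests.* Protocol 7.4 says "Laboratory tests with values within the clinically significant range will be repeated during the same visit whenever possible". This depends on Table 6.4, which has rows for creatinine, BUN, WBC and hemoglobin but none for CK or cystatin C. A triggering value from a scheduled visit stays in the table, and a repeat in the same visit may count as scheduled data. Repeats drawn elsewhere after the subject has left would be unscheduled.
- *Extended steroid treatment.* Protocol 6.3 says "The duration of treatment will be determined based on weekly levels of GGT and immune responses". This yields extra GGT values, which eDISH covers, so it adds nothing to the gap.
- *Brown urine or muscle pain.* Protocol 11.3.2.11 names no tests. That CK and renal tests would be drawn is a reasonable inference, not protocol text.

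**Step 3. How often would a scheduled draw meet a short rise?**

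The documents give no figure here, so there is none to reproduce. This is an illustration.

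Inputs: Protocol 6.4 and Table 2 place full safety labs on Days 0, 1, 2, 7, 14, 30, 60, 90 and 180, and at 12, 18 and 24 months (taken as Days 365, 548 and 730). Days 45 and 75 are GGT only, and month 9 has no safety labs. Assumptions: onset is uniform over the stated period and the rise lasts D days.

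Formula: capture = sum over gaps of min(D, gap) ÷ total days.

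From Day 30 the gaps are 30, 30, 90, 185, 183 and 182 days, which sum to 700. All exceed 21 days, so for D up to 21 capture = 6D/700.

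- D = 7: 42/700 = 6.0%, missed 94.0%
- D = 14: 84/700 = 12.0%, missed 88.0%
- D = 21: 126/700 = 18.0%, missed 82.0%

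Sensitivity to the start date: from Day 2 three more gaps (5, 7 and 16 days) enter, and the total is 728 days.

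- D = 7: (5 + 8×7)/728 = 61/728 = 8.4%
- D = 14: (5 + 7 + 7×14)/728 = 110/728 = 15.1%

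Within Days 2 to 30 alone, capture is (5 + 7 + 7)/28 = 67.9% for 7 days and (5 + 7 + 14)/28 = 92.9% for 14 days. The gap is therefore a feature of later follow-up, not of the first month.

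The visit windows in Protocol 6.8 move draw dates but add no draws. Meeting a rise is also not the same as recording its peak, since a scheduled draw may fall on the way up or down.

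**The case against.** A reader might infer that these results drop out of the primary safety analysis altogether, or that rhabdomyolysis is summarised nowhere. The documents do not support either reading.

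- SAP 6.6.2.1 and 6.6.2.1.2 plan TEAE tables for rhabdomyolysis (SMQ Rhabdomyolysis/myopathy, broad and narrow terms): all events, treatment-related events, maximum severity and serious events. These count subjects with any event and are not tied to visits. Acute kidney injury is also tabulated, although within the hypersensitivity risk group.
- All laboratory data in the eCRF are listed by cohort and subject. With 1 + 3 + 3 = 7 subjects, such a listing can be read in full.
- Protocol 12.1 gives the DSMB a summary of clinically significant laboratory results.
- Liver peaks are kept by eDISH. ALT may also carry some muscle signal, since Protocol 6.4 notes that it is raised in muscular dystrophy.
- Restricting by-visit tables to scheduled draws is sound practice, because mixing event-triggered values into visit means would distort them.

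All of this stands, and it limits the point to a reporting gap. It does not close the gap. AE tables count coded events by grade and report no CK or creatinine level. A listing is not a summary, and the DSMB report is not an SAP output. The case for scheduled-only visit means is no argument against a separate worst-value display.

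**Conclusion.** The point holds for the laboratory endpoint, not for the safety analysis as a whole. Under the SAP as written, an unscheduled peak in CK, creatinine, cystatin C, BUN, WBC or hemoglobin enters no laboratory summary or plot. Liver tests are handled better, although the study's own experience points to muscle.

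The 88% to 94% figure is an illustration. It rests on a 7- to 14-day rise and uniform onset over Days 30 to 730, neither of which the documents supply, and it falls to about 85% to 92% if onset is counted from Day 2. It describes rises that only an unscheduled draw could document; whether such a draw is made is inferred. The absence of a display follows directly from SAP 5.1 and 6.6.3 and needs none of these assumptions.

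With seven subjects and full listings this is a moderate weakness. It is worth correcting because the correction is small.

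**What to change.** Leave the by-visit tables on scheduled visits. In SAP 6.6.3 add:

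1. A worst post-baseline summary per test, by cohort and overall, using scheduled and unscheduled results. Include CK, creatinine and cystatin C, shown as multiples of baseline or of the local laboratory's ULN.
2. The number of subjects out of N with any post-baseline value in the Table 6.4 clinically significant range, for the tests that have one. This covers creatinine and BUN but cannot cover CK or cystatin C, which item 1 must carry.
3. CK, creatinine and cystatin C in the per-subject line plots, with unscheduled results shown.

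It would also help to say which value the by-visit table uses when a test is repeated within a visit, and to confirm that off-site repeats reach the eCRF. Protocol 7.4 files these in the research chart, while Protocol 13.1 says source data are transferred to the database.

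The cost is SAP wording, two tables, the added plots and a little programming. Local-laboratory values need ULN scaling before they are combined.
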